5.8.4. Prohibited Medications

Prohibited drugs and dietary supplements not otherwise specified herein or in [Appendix 4](#) must be discontinued at least 30 days or 5 half-lives (whichever is longer) before the first dose of investigational product. A list of prohibited drugs with specific discontinuation recommendations can be found in [Appendix 4](#).

- Any DMARDs (synthetic or biologic) except for methotrexate or sulfasalazine. Subjects receiving any other investigational or marketed treatment for AS, arthritis or back pain other than permitted in [Appendix 4](#). Subjects receiving any other investigational drug during the study.
- Injected (intravenous, intramuscular, intraarticular or epidural) corticosteroids are not allowed during the blinded portion of the study either as a stable concomitant medication or as rescue medication.
- Herbals with pharmaceutical properties are allowed only if there is acceptable evidence of no CYP3A inhibition or induction and must be reported as a concomitant medication. Otherwise, herbals with pharmaceutical properties must be discontinued for at least 4 weeks prior to first dose of study drug, unless there is sufficient data available regarding the duration of an herbal medication’s pharmacokinetic and pharmacodynamic effects to allow a shorter washout to be specified (eg, 5 half-lives).
- Vaccinations with live components are prohibited during the study and for 6 weeks after last dose of investigational product.
- Currently receiving or previously used thalidomide.

- Acetaminophen/paracetamol is not permitted as a part of combination products such as over-the-counter “cold remedies” or in combination with opioids if the acetaminophen/paracetamol dose will exceed 2.6 gm/day.

6. STUDY PROCEDURES

6.1. Screening

Subjects will be screened within 30 days prior to administration of investigational product to confirm that they meet the entrance criteria for the study.

Rescreening of subjects will be allowed in a limited number of circumstances as determined by the Pfizer Medical Monitor (eg, requires antimicrobial therapy within 2 weeks prior to the first dose of investigational product, requires emergency surgery) and should be confirmed with the Pfizer Medical Monitor when rescreening can occur.

The study investigator or a sub-investigator will discuss with each subject the nature of the study, its requirements, and its restrictions. Written informed consent/assent must be obtained prior to performance of any protocol-specific procedures.

Subjects, who are on prohibited medications and are deriving a beneficial response from the medication, should not be entered into this study. However, there may be subjects taking a prohibited medication who have experienced an ineffectual/suboptimal response or side effects and wish to enter the study. These subjects may require a washout period that extends beyond the screening duration. For these subjects, written informed consent and a unique subject number obtained through the IRT system must be obtained prior to initiation of the washout period. No other screening activities should be performed at this time. These subjects should return for a Screening visit within the allowed window, at which time all screening procedures should be completed.

At all visits, subjects should complete the “Patient Reported Outcome” (PRO) questionnaires at the clinic prior to any other study procedures outside of the informed consent process.

The following procedures will be performed:

- Informed consent;
- Collect demographic information (sex, date of birth, race, and ethnicity);
- ASAS/ASDASCRP Component: “Patient Global Assessment of Disease” (NRS), “Patient Assessment of Spinal Pain” which include Total Back Pain(NRS) and Nocturnal Spinal Pain (NRS), BASDAI (NRS), BASFI (NRS);
- Confirmation of diagnosis of active AS: based on the Modified New York Criteria for Ankylosing Spondylitis (1984) and BASDAI score of ≥ 4 and back pain score (BASDAI Question 2) of ≥ 4 ;

- General Medical History: Should include history of previous vaccinations, specifically influenza, pneumococcal and herpes zoster as well as family history of AS, herpes zoster history, CV risk factor assessment, smoking history and average weekly alcohol consumption;
- Specific Medical History: History of uveitis, psoriasis, inflammatory bowel disease and peripheral articular involvement as assessed by swollen joint count;
- Prior/Concomitant treatments: Current and prior medications (noting exclusions and required csDMARD restrictions), including a complete history of all DMARDs (synthetic/biologic) ever taken with reasons for discontinuation (those taken during the 1 year prior to the first dose of investigational product should include the dose and duration of treatment). Complete history of all drugs (including non-prescription drugs, vitamins and dietary supplements) taken within 4 weeks prior to the screening procedures;
- Vital Signs: Blood pressure (seated), pulse rate and temperature (via tympanic, oral or temporal, preferred);
- Complete Physical Examination: General appearance, skin (presence of rash), HEENT (head, eyes, ears, nose and throat), lungs (auscultation), heart (auscultation for presence of murmurs, gallops, rubs), lower extremities (presence of peripheral edema), abdominal (palpation and auscultation), neurologic (mental status, station, gait, reflexes, motor and sensory function, coordination) and lymph nodes;
- Height, weight (without shoes preferred);
- 12-lead electrocardiogram submitted to central reader;
- BASMI (linear function) obtained by qualified blinded assessor: Lateral spinal flexion, tragus-to-wall distance, lumbar flexion (modified Schober), maximal intermalleolar distance and cervical rotation;
- Spinal Mobility obtained by qualified blinded assessor: chest expansion;
- Laboratory testing: Central laboratory tests include: Hematology, Urinalysis, Chemistry Panel, HIV Serology, hepatitis testing (HBsAg, HBcAb, HCV Ab), high sensitivity C-Reactive Protein (hsCRP), and Prothrombin time (PT/INR); FSH and hepatitis reflex testing, if applicable. Screening lab tests as noted in the inclusion/exclusion criteria may be repeated a single time if the initial result is inconsistent with previous subject laboratory history;
- Urine Pregnancy Test (for women of childbearing potential only);

- QuantiFERON®-TB Gold: Must be performed unless previously tested and documented within 3 months of screening visit OR unless subject has previously received an adequate course of therapy for either latent or active TB infection;
- Radiograph of chest: Unless performed within 3 months of Screening visit and documented;
- Radiograph of SI joints (read centrally). If documentation of AS has been obtained with prior radiographs, obtain radiographs for submission to the central reader. If not, perform after all other screening procedures and only perform radiograph of SI joints if subject does not fail to meet other study criteria;
- If radiographs are not available or unable to be read by the central reader, new radiograph (AP pelvis) should be obtained at the Screening visit and submitted to the central reader;
- Monitoring for adverse events;
- Contraception check: Confirm and document that proper contraception is being used.

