1.2.3.2. Potential Risks

The risks associated with tofacitinib are similar to the risks associated with the use of other bDMARDs, including a potential risk for development of serious and other infections, eg, tuberculosis and viral reactivation such as herpes zoster (HZ). In the RA program, the serious infection rate in the tofacitinib-treated subjects was consistent with the rates of serious infections in patients treated with other therapeutic interventions including bDMARDs. Serious infections were more frequent among the elderly (>65 years), subjects with diabetes mellitus and subjects treated previously with biological agents. Rates of HZ infections in tofacitinib-treated subjects with RA were increased compared with placebo-treated RA subjects and historical controls; this included an increased risk of HZ infections in Asian RA subjects compared with non-Asian RA subjects. In the tofacitinib RA clinical development program, the rate of HZ varied significantly across countries and regions. The incidence rates of HZ in Japan and Korea were notably higher than the rates observed in other regions/countries. The reason for the increased risk of HZ in Japan and Korea is unclear.

Decreases in white blood cell counts, particularly neutrophils and lymphocytes, and decreased hemoglobin have been observed. These effects are usually mild to moderate and returned to normal after discontinuation of therapy. Anemia is a possible consequence of JAK2 inhibition. Experience to date indicates that anemia is easily monitored, usually manageable without discontinuation of treatment, and reversible on discontinuation of tofacitinib. Neutropenia is of primary concern by virtue of its relationship to an increased risk of infection. Thus far no association between the occurrence of neutropenia and infection has been observed in the tofacitinib program.

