13. Subjects receiving non-prohibited concomitant medications for any reason must be willing to stay on a stable regimen (doses and frequency) as defined in the protocol.
14. No evidence of active or latent or inadequately treated infection with *Mycobacterium tuberculosis* (TB) as defined by **all** of the following:
- A negative QuantiFERON[®]-TB Gold (QFT G) In Tube test performed at or within 3 months prior to the Screening visit. Subjects with a history of Bacille Calmette Guérin (BCG) vaccination will be tested with the QFT G test;
 - No local QFT G testing will be accepted for meeting this inclusion criterion;

- A chest radiograph taken at or within the 3 months prior to screening and reviewed by a radiologist or pulmonologist as per local standard of care and documented to be without changes of suggestive active TB infection;
- No history of either untreated or inadequately treated latent or active TB infection.

NOTE: If a subject has previously received an adequate course of therapy for latent (eg, 9 months of isoniazid in a locale where rates of primary multi drug resistant TB infection are <5% or an acceptable alternative regimen) TB infection, a QuantiFERON®-TB Gold In Tube (QFT Gold test) need not be obtained, but a chest radiograph must still be obtained if not done so within the prior 3 months. A subject who is currently being treated for latent TB infection can only be enrolled with confirmation of current incidence rates of multi drug resistant TB infection and documentation of an adequate treatment regimen.

15. Women of childbearing potential must test negative for pregnancy prior to enrollment in this study.

16. Female subjects of non-childbearing potential must meet at least 1 of the following criteria:

- Achieved post-menopausal status, defined as follows: cessation of regular menses for at least 12 consecutive months with no alternative pathological or physiological cause; status may be confirmed with/and have a central laboratory confirmation of serum follicle-stimulating hormone (FSH) level confirming the postmenopausal state;
- Have undergone a documented hysterectomy and/or bilateral oophorectomy;
- Have medically confirmed ovarian failure.

All other female subjects (including female subjects with tubal ligations) are considered to be of childbearing potential.

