4.3. Randomization Criteria

A subject who has signed an informed consent document to participate in the study, has undergone all screening procedures, and has met all inclusion and none of the exclusion criteria for participation in the study at the Baseline visit.

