7.1.8. TB Testing

During the Screening period, it must be determined and documented that a subject does not have evidence of active or latent or inadequately treated infection with *Mycobacterium tuberculosis* (TB) per the inclusion criteria. The results of TB screening conducted in the 3 months prior to Screening or during the Screening period must be documented in study records prior to Baseline/Day 1.

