7.1.10. Chest Radiograph

A chest radiograph will be obtained at the Screening visit in all subjects unless it has been previously taken and documented within the 3 months prior. To be considered eligible for the study, the radiograph must be reviewed by a radiologist or pulmonologist as per local standard of care and documented as negative for active tuberculosis infection.

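### Protocol Section 6.1 waives the QuantiFERON test after treated active TB, but inclusion criterion 14 waives it only after treated latent TB

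*Protocol*

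**What the plan says.** Criterion 14 in Protocol Section 4.1 asks for no evidence of active, latent or inadequately treated TB, and lists conditions that must all be satisfied. The first is a negative QuantiFERON Gold "In Tube test performed at or within 3 months prior to the Screening visit"; results from a local laboratory do not count. Another is a chest radiograph without signs of active TB. The last is "No history of either untreated or inadequately treated latent or active TB infection".

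The note to criterion 14 contains the only exemption from the test. It opens "If a subject has previously received an adequate course of therapy for latent", gives an isoniazid example, and completes the phrase with TB infection. Active TB is not named. The note keeps the chest radiograph requirement for exempted subjects.

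The screening procedures in Section 6.1 state the exemption differently. There the QuantiFERON must be done unless a result from the previous 3 months is documented, or "unless subject has previously received an adequate course of therapy for either latent or active TB infection".

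**The concern.** The two sections define the exempt group differently, and the extra group in Section 6.1 is people who have had active TB. A site using Section 6.1 as its checklist could leave out a test that the eligibility criterion requires, and randomize a subject for whom criterion 14 has not been shown to be met.

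This is a safety-screening matter. Section 1.2.3.2 lists serious infections among the risks of tofacitinib, "eg, tuberculosis and viral reactivation such as herpes zoster". Section 6 is also where the Schedule of Activities sends sites for the detail of each required procedure, so the wording is an operating instruction and not background text.

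**Working it through.** No arithmetic applies; the check compares the texts.

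**1. Does the affected subject exist under the protocol?** The history condition of criterion 14 excludes untreated or inadequately treated TB, latent or active. It does not exclude adequately treated active TB. A subject with that history passes the condition and comes to the QuantiFERON requirement.

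**2. What does each text require, by TB history?** (Assuming no documented QuantiFERON result from the previous 3 months.)

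| TB history | Criterion 14 (Section 4.1) | Section 6.1 | Agree? |
|---|---|---|---|
| None | Negative test required | Test required | Yes |
| Latent, adequately treated | Test waived | Test waived | Yes |
| Active, adequately treated | Negative test required | Test waived | **No** |
| Untreated or inadequately treated | Not eligible | Not applicable | Yes |

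The conflict is confined to the third row.

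**3. Does another section supply the wider waiver?** None does.

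- The Schedule of Activities and the laboratory table in Section 7.1 list QuantiFERON at Screening with no exception for treated active TB.
- Section 7.1.8 refers back to the inclusion criteria.
- Section 7.1.9 deals with indeterminate results and annual retesting in high-incidence countries, not with this exemption.

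**4. Which text governs?** Criterion 14 does.

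- Section 4.1 requires every inclusion criterion to be met.
- Section 4.3 allows randomization only of a subject who "has met all inclusion and none of the exclusion criteria for participation in the study at the Baseline visit".
- Section 6.2 repeats the condition for entry to the study period.
- Section 7.1.8 requires TB status to be settled against the inclusion criteria, with results that "must be documented in study records prior to Baseline/Day 1".

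Section 6.1 describes screening as the means of confirming the entrance criteria, so it cannot relax them. This settles the direction of the correction from current text. The amendment log (Amendment 1, item 20) records that the TB criterion was changed with respect to subjects treated for active TB. That would explain a leftover phrase in Section 6.1, but the argument does not rely on it.

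**5. What follows if the test is omitted?** The chest radiograph must still be reviewed and "documented as negative for active tuberculosis infection" (Section 7.1.10), and the bar on untreated or inadequately treated TB remains. SAP Section 4.2.2 does not list criterion 14 among the deviations that remove a subject from the per-protocol set. The full analysis set depends only on randomization and dosing (SAP Section 4.1). Sample size, power and type I error are not involved.

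**The case against.** The strongest reply is that the conflict resolves itself. Section 6.1 sets no eligibility rule and does not forbid the test. Sections 4.1, 4.3, 6.2 and 7.1.8 all lead back to criterion 14, so a site that checks eligibility properly would find the missing result. Harm needs three things together: a subject with treated active TB, a site that relies on Section 6.1 alone, and failure of the later checks.

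The amendment log entry is also ambiguous. It could mean that such subjects were to be excluded altogether, in which case a waived test would not matter for them. The sponsor might equally have wanted the wider waiver and failed to put it in the note.

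Finally, the wording change may come too late. The Amendment 3 check for venous thromboembolism risk applies at every remaining visit, yet the Schedule of Activities shows it only from Week 32 onward, which suggests that screening had finished.

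Most of this stands as a limit on importance. It does not make the texts agree. A clear order of precedence tells us which text is wrong, but the wrong instruction remains in the section that sites are told to follow. The log's ambiguity does not matter, because the current criterion as written does not exclude adequately treated active TB. If the sponsor did intend the wider waiver, criterion 14 would have to change instead; one of the two texts needs correction either way.

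**Conclusion.** The concern holds. For a subject with adequately treated active TB, Section 6.1 waives a test that criterion 14 requires, and Section 6.1 is the text in error because the inclusion criteria govern.

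The matter is minor. It involves one screening test in one category of subject. The number affected cannot be estimated, because the documents give no count of subjects with prior active TB. There is no bearing on the efficacy conclusions.

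The finding of a mismatch rests only on current text. Two further points are inferences: that the phrase is a remnant of older wording, and that enrolment has ended under this version.

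**What to change.** In Section 6.1, remove the reference to active TB so that the waiver covers adequately treated latent TB only, as in the note to criterion 14. If the sponsor wants the wider waiver, it should add treated active TB to that note and justify it.

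If screening is still open, send sites a short clarification. In either case, list enrolled subjects with a history of active TB and confirm that each has an acceptable negative QuantiFERON on file. If enrolment has closed, this check is the only part with practical value.

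The cost is a deletion of a few words, a letter to sites and a brief data check. With screening open, a few more tests would be done, and possibly a few more subjects would fail screening.

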6.2. Study Period

Subjects who have met all the inclusion criteria and have no exclusion criteria present may participate in the study. Blood collection for laboratory testing requiring a fasting state (at least 9 hours) may be taken up to 48 hours prior to the Baseline/Day 1 visit. For post-baseline double-blind study period visits blood collection for laboratory testing requiring a fasting state (at least 9 hours) up to 48 hours prior to or following as necessary to ensure samples are collected in a fasting state. If the subject has not fasted for at least 9 hours, the visit should be rescheduled to occur within 48 hours in the fasting state.

Subjects will complete the PRO questionnaires at the clinic prior to any other study procedures. This sequence of study procedures will reduce the risk of inadvertently introducing bias in a subject's responses through study staff interactions. In the unlikely event that a PRO questionnaire(s) is not able to be administered by the study site staff and completed by the subject at the clinic visit, the PRO questionnaire(s) should not be administered.

6.2.1. Baseline Day 1 (Randomization)

Subjects are required to fast for at least 9 hours prior to the, visit; however, blood collection for laboratory testing may be taken up to 48 hours prior to the Baseline/Day 1 visit as necessary to ensure the samples are collected in a fasting state. If the blood collection is completed in advance of the clinic visit, the PROs should not be done with the blood collection but at the clinic visit.

- All PROs should be performed before any other study procedures at the clinic visit. These include the following: ASAS/ASDASCRP Component: “Patient Global Assessment of Disease (NRS)”, “Patient Assessment of Spinal Pain” which includes Total Back Pain (NRS) and Nocturnal Spinal Pain (NRS), BASDAI (NRS), BASFI (NRS), ASQoL, SF-36v2, EuroQol EQ-5D Health State Profile 3 Level (EQ-5D-3L) and Your own health state today (EQ-VAS), Functional Assessment of Chronic Illness Therapy-Fatigue Scale (FACIT-F), - WPAI and AS HealthCare Resource Utilization Questionnaire (AS-HCRU) Questionnaire.

[figure not shown]
Prior to the first dose the following procedures will be completed:

- Confirmation of diagnosis of active AS: based on the Modified New York Criteria for Ankylosing Spondylitis (1984) and BASDAI score of ≥ 4 and back pain score (BASDAI Question 2) of ≥ 4 ;
- Determination and confirmation of either “bDMARD-naive” or “TNFi-IR” or “bDMARD use (non-IR)” status for randomization;
- Prior/Concomitant treatments: Current and prior medications (noting exclusions and required DMARD restrictions) will be reviewed to ensure no concomitant medications (including non-prescription drugs, vitamins and dietary supplements) have been added that are prohibited;
- Vital Signs: Blood pressure (seated), pulse rate and temperature (via tympanic, oral or temporal, preferred);
- Complete Physical Examination: General appearance, skin (presence of rash), HEENT (head, eyes, ears, nose and throat), lungs (auscultation), heart (auscultation for presence of murmurs, gallops, rubs), lower extremities (presence of peripheral edema), abdominal (palpation and auscultation), neurologic (mental status, station, gait, reflexes, motor and sensory function, coordination) and lymph nodes;
- Weight (without shoes preferred) and waist circumference;
- Specific Medical History: History of uveitis, psoriasis, inflammatory bowel disease and peripheral articular involvement as assessed by swollen joint count;
- BASMI (linear function) obtained by qualified blinded assessor: Lateral spinal flexion, tragus-to-wall distance, lumbar flexion (modified Schober), maximal intermalleolar distance and cervical rotation;
- Spinal mobility obtained by qualified blinded assessor: chest expansion;
- Laboratory testing: Central laboratory tests include: Hematology, Urinalysis, Chemistry Panel, Lipid Profile (fasting), Urine Pregnancy Test (for women of childbearing potential only), hsCRP;

- Blood sample for HLA-B27;
- Blood sample for Fluorescence Activated Cell Sorting (FACS) Analysis;
- Assessment of swollen joints (44-joint count) by qualified blinded assessor;
- Assessment of enthesitis using the Maastricht Ankylosing Spondylitis Enthesitis Score (MASSES) Index by qualified blinded assessor;
- Contact Interactive Web Response System (IWRS) to randomize subject;
- Dispense the investigational product to subject as described in [Section 5.5](#) and as noted in the [Administration](#) and Compliance Sections. Instruct subject on correct investigational product administration. All subsequent scheduled doses on clinic visit days will be taken in the clinic;
- Monitoring for adverse events;
- Contraception check: Confirm and document that proper contraception is being used;
- Instruct subject not to take the in-clinic dose of investigational product the day of the next study visit and to bring the drug supply with them to the visit.

6.2.2. Week 2

There is a ± 3 day window for this visit.

- All PROs should be completed prior to any other study procedures. These include the following: ASAS/ASDASCRP Component: “Patient Global Assessment of Disease (NRS)”, “Patient Assessment of Spinal Pain” which includes Total Back Pain (NRS) and Nocturnal Spinal Pain (NRS), BASDAI (NRS), BASFI (NRS), and FACIT-F.

After the PROs have been obtained, the following procedures should be completed:

- Verify morning dose of investigational product was not administered by subject. If the dose was administered, continue with visit but re-instruct subject on the requirement for in-clinic dosing;

Note: For subjects where the visit is conducted in the afternoon or evening, verify the afternoon or evening dose of investigational product was not administered by the subject.

- Targeted physical examination (examination of heart, lungs, abdomen, lower extremities, skin (presence of rash) and lymph nodes);
- Weight (without shoes preferred);
- BASMI (linear function) obtained by qualified blinded assessor: Lateral spinal flexion, tragus-to-wall distance, lumbar flexion (modified Schober), maximal intermalleolar distance and cervical rotation;
- Spinal mobility obtained by qualified blinded assessor: chest expansion;
- Vital signs: Blood pressure (seated), pulse rate and temperature (via tympanic, oral or temporal, preferred);
- Laboratory testing: Urine Pregnancy Test (for women of childbearing potential only), hsCRP;
- Assessment of swollen joints (44-joint count) by qualified blinded assessor;
- Administer investigational product from the previously dispensed study drug supplies unless subject had already administered dose at home;
- Complete drug accountability;
- Monitoring of adverse events and concomitant treatments. Record any modifications, deletions or additions;
- Contraception check: Confirm and document that proper contraception is being used;
- Instruct subject not to take the in-clinic dose of investigational product the day of the next study visit and to bring the drug supply with them to the visit.

6.2.3. Week 4

There is a ± 3 day window for this visit.

Subjects are required to fast for at least 9 hours prior to the visit; however, blood collection for laboratory testing may be taken up to 48 hours prior to or following this visit as necessary to ensure the samples are collected in a fasting state. If the blood collection is completed in advance of the clinic visit, the PROs should not be done with the blood collection but at the clinic visit.

- All PROs should be completed prior to any other study procedures. These include the following: ASAS/ASDAS_{CRP} Component: “Patient Global Assessment of Disease (NRS)”, “Patient Assessment of Spinal Pain” which includes Total Back Pain (NRS) and Nocturnal Spinal Pain (NRS), BASDAI (NRS), BASFI (NRS), and FACIT-F.

After the PROs are obtained, the following procedures should be completed prior to dosing:

- Verify morning dose of investigational product was not administered by the subject and previous day’s dosing was administered;

Note: For subjects where the visit is conducted in the afternoon or evening, verify the afternoon or evening dose of investigational product was not administered by the subject.

- Vital signs: Blood pressure (seated), pulse rate and temperature (via tympanic, oral or temporal, preferred);
- Laboratory testing: Central laboratory tests include: Hematology, Urinalysis, Chemistry Panel, Lipid Profile (fasting), Urine Pregnancy Test (for women of childbearing potential only), hsCRP;
- [REDACTED]
- Blood sample for FACS Analysis;
- [REDACTED]

The following procedures can be done before or after dosing depending upon the clinic’s schedule but is recommended that they be done at the same time (before or after dosing) consistently across all subsequent subject clinic visits:

- Targeted physical examination (examination of heart, lungs, abdomen, lower extremities, skin (presence of rash) and lymph nodes);
- Weight (without shoes preferred);
- BASMI (linear function) obtained by qualified blinded assessor: Lateral spinal flexion, tragus-to-wall distance, lumbar flexion (modified Schober), maximal intermalleolar distance and cervical rotation;
- Spinal mobility obtained by qualified blinded assessor: chest expansion;
- Assessment of swollen joints (44-joint count) by qualified blinded assessor;
- Assessment of enthesitis using the MASES Index by qualified blinded assessor;
- Complete drug accountability.

Procedures to be performed after dosing:

- [REDACTED]
- Contact IWRS and dispense new supply of investigational product to subject;
- Monitoring of adverse events and concomitant treatments. Record any modifications, deletions or additions;
- Contraception check: Confirm and document that proper contraception is being used;
- Instruct subject not to take the in-clinic dose of investigational product the day of the next study visit and to bring the drug supply with them to the visit.

6.2.4. Week 8

There is a ± 7 day window for this visit.

[REDACTED]

- All PROs should be completed prior to any other study procedures. These include the following: ASAS/ASDASCRP Component: “Patient Global Assessment of Disease (NRS)”, “Patient Assessment of Spinal Pain” which includes Total Back Pain (NRS) and Nocturnal Spinal Pain (NRS), BASDAI (NRS), BASFI (NRS), and FACIT-F.

After the PROs have been obtained, the following procedures should be completed:

- Verify morning dose of investigational product was not administered by the subject and previous day’s dosing was administered;

Note: For subjects where the visit is conducted in the afternoon or evening, verify the afternoon or evening dose of investigational product was not administered by the subject.

- Vital signs: Blood pressure, pulse rate and temperature (via tympanic, oral or temporal, preferred);
- Laboratory testing: Urine Pregnancy Test (for women of childbearing potential only), hsCRP;

- [REDACTED]

- [REDACTED]

The following procedures can be done before or after dosing depending upon the clinic's schedule but it is recommended that they be done at the same time (before or after dosing) consistently across all subsequent subject clinic visits:

- Targeted physical examination (examination of heart, lungs, abdomen, lower extremities, skin (presence of rash) and lymph nodes);
- Weight (without shoes preferred);
- Specific Medical History: History of uveitis, psoriasis, inflammatory bowel disease and peripheral articular involvement as assessed by swollen joint count;
- BASMI (linear function) by qualified blinded assessor: Lateral spinal flexion, tragus-to-wall distance, lumbar flexion (modified Schober), maximal intermalleolar distance and cervical rotation;
- Spinal mobility obtained by qualified blinded assessor: chest expansion;
- Assessment of swollen joints (44-joint count) by qualified blinded assessor;
- Assessment of enthesitis using the MASES Index by qualified blinded assessor;
- Complete drug accountability.

After dosing:

- 
- Monitoring of adverse events and concomitant medications. Record any modifications, deletions or additions;
- Contraception check: Confirm and document that proper contraception is being used;
- Contact IWRS and dispense new supply of investigational product to subject;
- Instruct subject not to take the in-clinic dose of investigational product the day of the next study visit and to bring the drug supply with them to the visit.

6.2.5. Week 12

There is a ± 7 day window for this visit.

- All PROs should be completed prior to any other study procedures. These include the following: ASAS/ASDASCRP Component: "Patient Global Assessment of Disease (NRS)", "Patient Assessment of Spinal Pain" which includes Total Back Pain (NRS) and Nocturnal Spinal Pain (NRS), BASDAI (NRS), BASFI (NRS), and FACIT-F.

After the PROs are obtained, the following procedures should be completed prior to dosing:

- Verify morning dose of investigational product was not administered by subject. If the dose was administered, continue with visit but re-instruct subject on the requirement for in-clinic dosing;

Note: For subjects where the visit is conducted in the afternoon or evening, verify the afternoon or evening dose of investigational product was not administered by the subject.

- Vital signs: Blood pressure (seated), pulse rate and temperature (via tympanic, oral or temporal, preferred);
- Laboratory testing: Hematology, Chemistry Panel, Urinalysis, Urine Pregnancy Test (for women of childbearing potential only), hsCRP;
- Administer in-clinic dose of investigational product from previously dispensed study drug supplies.

The following procedures can be done before or after dosing depending upon the clinic's schedule but it is recommended that they be done at the same time (before or after dosing) consistently across all subsequent subject clinic visits:

- Targeted physical examination (examination of heart, lungs, abdomen, lower extremities, skin (presence of rash) and lymph nodes);
- Weight (without shoes preferred);
- BASMI (linear function) by qualified blinded assessor: Lateral spinal flexion, tragus-to-wall distance, lumbar flexion (modified Schober), maximal intermalleolar distance and cervical rotation;
- Spinal mobility obtained by qualified blinded assessor: chest expansion;
- Assessment of swollen joints (44-joint count) by qualified blinded assessor;
- Assessment of enthesitis using the MASES Index by qualified blinded assessor;
- Complete drug accountability.

After dosing:

- Monitoring of adverse events and concomitant treatments. Record any modifications, deletions or additions;
- Contraception check: Confirm and document that proper contraception is being used;

- Contact IWRS and dispense new supply of investigational product to subject;
- Instruct subject not to take the in-clinic dose of investigational product the day of the next study visit but to bring the drug supply with them to the visit.

6.2.6. Week 16

There is a ± 7 day window for this visit.

Subjects are required to fast for at least 9 hours prior to the visit; however, blood collection for laboratory testing may be taken up to 48 hours prior to or following this visit as necessary to ensure the samples are collected in a fasting state. If the blood collection is completed in advance of the clinic visit, the PROs should not be done with the blood collection but at the clinic visit.

- All PROs should be performed before any other study procedures at the clinic visit. These include the following: ASAS/ASDAS_{CRP} Component: “Patient Global Assessment of Disease (NRS)”, “Patient Assessment of Spinal Pain” which includes Total Back Pain (NRS) and Nocturnal Spinal Pain (NRS), BASDAI (NRS), BASFI (NRS), ASQoL, SF-36v2, EQ-5D-3L and EQ-VAS, FACIT-F, - WPAI and AS-HCRU Questionnaire.
- Verify morning dose of investigational product was not administered by subject. If the dose was administered, continue with visit but re-instruct subject on the requirement for in-clinic dosing;

Note: For subjects where the visit is conducted in the afternoon or evening, verify the afternoon or evening dose of investigational product was not administered by the subject.

- Blood pressure (seated), pulse rate and temperature (via tympanic, oral or temporal, preferred);
- 12-lead electrocardiogram submitted to central reader;
- Laboratory testing: Central laboratory tests include: Hematology, Urinalysis, Chemistry Panel, Lipid Profile (fasting), Urine Pregnancy Test (for women of childbearing potential only), hsCRP;
- Blood sample for FACS Analysis;
- Complete Physical Examination: General appearance, skin (presence of rash), HEENT (head, eyes, ears, nose and throat), lungs (auscultation), heart (auscultation for presence of murmurs, gallops, rubs), lower extremities (presence of peripheral edema), abdominal (palpation and auscultation), neurologic (mental status, station, gait, reflexes, motor and sensory function, coordination) and lymph nodes;

- Weight (without shoes preferred);
- Specific Medical History: History of uveitis, psoriasis, inflammatory bowel disease and peripheral articular involvement as assessed by swollen joint count;
- BASMI (linear function) by qualified blinded assessor: Lateral spinal flexion, tragus-to-wall distance, lumbar flexion (modified Schober), maximal intermalleolar distance and cervical rotation;
- Spinal mobility obtained by qualified blinded assessor: chest expansion;
- Assessment of swollen joints (44-joint count) by qualified blinded assessor;
- Assessment of enthesitis using the MASES Index by qualified blinded assessor; Complete drug accountability;
- Monitoring of adverse events and concomitant treatments. Record any modifications, deletions or additions;
- Contraception check: Confirm and document that proper contraception is being used;

